Participants at a given performance site who meet all inclusion/exclusion criteria will be randomized using Randomize.net or a similar randomization methodology as endorsed by the Michigan Institute for Clinical & Health Research (MICHR). Subjects will be randomized to either silicone or non-silicone ureteral stent placement at a 1:1 allocation ratio. Blocked, stratified randomization based upon surgeon classified stone location (renal only versus ureteral), with random block sizes will be used to ensure group balance. Randomization list will be determined separately in strata defined by state the stratification factor/s here. The randomization code will be generated by an independent statistician.

At the time of surgery, if baseline PRO has been completed, prior to placement of the stent, the surgeon will be notified via email/text message and the surgeons operating room staff can reference the MUSIC registry to confirm if the patient should have a silicone vs non-silicone stent based on random allocation by the BLUES study coordinator or another member of the BLUES study team. Only patients who are randomized, remain eligible prior to stent placement, and receive the study treatment will be counted towards the treatment population of 224 participants. These patients will receive PRO questionnaires, via the ROCKS PRO infrastructure, pre-operatively and at 7 days, and 4 weeks after surgery. If the patient is unable to complete the PRO questionnaires through the ROCKS PRO infrastructure, the patient may complete an email survey via REDCap, survey by phone from a BLUES study team member, or paper questionnaires. Patients will also receive text messages which include pain-specific questionnaires to be completed daily for 10 days after surgery. The process of completing the ROCKS PRO questionnaire is

the same, regardless of the patient's participation in the BLUES study. A patient can withdraw or decline participation in BLUES and/or ROCKS PRO at any time.

Section 8: TREATMENT PLAN

Section 8.1: Treatment overview

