An interim analysis for futility is planned after accrual of 112 patients. The study will stop early if it is found that the silicone stent arm has clinically significant worse pain intensity and worse pain interference at 7 days with worse pain defined as 5 or greater t-score points worse pain in the silicone stent arm compared to the non-silicone stent arm after adjusting for baseline. Under the alternative hypothesis for both endpoints simulations of 1000 trials estimates the probability of stopping early is 0%. If we assume that the silicone stent is worse than the non-silicone stent by 5 points simulation of 1000 trials estimates the probability of stopping early is 24.4%.

Section 11: STATISTICAL CONSIDERATIONS

Section 11.1: Statistical Hypotheses

This is a multi-center two-arm stratified, randomized comparative effectiveness study in patients are treated with URS for nephrolithiasis with a planned placement of a stent to assess patient reported quality of life. The primary hypothesis is that the silicone ureteral stent arm will have superior patient reported pain outcomes compared to the non-silicone stent arm. Patients will be stratified by stone location (kidney only / ureteral) and randomized to receive a silicone stent or a non-silicone stent and complete the PROMIS® pain intensity and PROMIS® pain interference surveys prior to surgery and at 7 days after stent placement.

Our formal statistical hypotheses are:

$$H_0: \mu_{ns} = \mu_{ss}, \quad H_1: \mu_{ns} \neq \mu_{ss}$$

where, μ_{ns} = mean PROMIS® pain intensity in non-silicone stent arm at 7 days

μ_{ss} = mean PROMIS® pain intensity in silicone stent arm at 7 days

AND

$$H_0: w_{ns} = w_{ss} \quad H_1: w_{ns} \neq w_{ss}$$

where, w_{ns} = mean PROMIS® pain interference in non-silicone stent arm at 7 days

w_{ss} = mean PROMIS® pain interference in silicone stent arm at 7 days

Section 11.2: Power/Sample Size:

Assume that the correlation of baseline is 0 for purposes of the sample size calculation. If this assumption is violated, the power for each hypothesis will be greater than the stated power.

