The primary endpoints of the study are PROMIS® pain intensity and PROMIS® pain interference t-scores. Each endpoint will be analyzed separately using an ANCOVA model for each. Using the MITT population for analysis, the t-score of the PROMIS® outcome at 7 days post-URS will be the dependent variable and treatment arm and pre-treatment (baseline) PROMIS t-score will be independent variables. The primary comparison of interest is treatment arm. The baseline adjusted mean pain score at 7-days will be reported by arm with the 97.5% confidence interval and a type-3 F-test will test the hypothesis that pain differs between the two treatment groups. Each endpoint modeled will test the effect of treatment arm adjusting for baseline with a type I error of 2.5% for an overall study type I error of 5%.

An analysis in the per-protocol population will be assess the robustness of the effect found in the primary analysis. Additionally, a multivariable model will be considered to account for other patient or surgical variables that may be unbalanced between the arms including timing of stent removal or stone location.

Analysis of the Secondary Endpoints

Additional health-related quality of life endpoints including PROMIS® Pain scores at 4 weeks will be analyzed with similar models described for the primary endpoint. A linear mixed model will be used to compare LURN SI-10 scores at 7 days and 4 weeks between treatment arms. Each analysis will report means with 95% confidence intervals at each time for each arm with a model based type-3 F-test comparing treatment arms.

Healthcare utilization within 30 days of URS will be assessed using a composite endpoint. The composite healthcare utilization metric within 30 days will be a composed score based upon utilization by the patient with each patient assigned a score based upon the highest utilization level that they participate in with levels defined in decreasing order:

5. Hospitalization and ICU care
4. Unplanned hospitalization
3. Emergency department visit
2. Ambulatory encounter: Clinic visit
1. Ambulatory encounter: Phone call or message

We will compare the composite score ranking between the treatment arms using a WinRatio analysis using the unmatched approach.(20) The median composite score for each arm will be reported, along with the WinRatio and associated 95% confidence interval and p-value.

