Abnormal imaging and stone-free rates will each be summarized as a count with the associated proportion by treatment arm and tested with a chi-square test (or fisher's exact test if event counts are 5 or less.)

Planned Interim Analyses

An interim analysis for futility is planned after accrual of 112 patients. The study will stop early if it is found that the silicon stent arm has clinically significant worse pain intensity and worse pain interference at 7 days with worse pain defined as 5 or greater t-score points worse pain in the silicone stent arm compared to the non-silicone stent arm after adjusting for baseline. Under the alternative hypothesis for both endpoints simulations of 1000 trials estimatas the probability of stopping early is 0%. If we assume that

the silicone stent is worse than the non-silicone stent by 5 points simulation of 1000 trials estimates the probability of stopping early is 24.4%.

Sub-Group Analyses

A sub-group analysis by stone location is planned. Primary and secondary endpoints will be reported for ureteral stones separately from renal stones.

Exploratory Analyses.

The mean (with standard deviation) or median (with interquartile range) days taken off work by patient and separately by caregiver will be compared between treatment arms with a t-test or Wilcoxon rank test if the distribution warrants.

Ecological Momentary Assessments of pain and PROMIS® daily ability to participate in social roles and activities score measured via daily text message will be displayed using spaghetti plots. Each measure will be analyzed with a linear mixed model including fixed effects of treatment arm, day, and the interaction of treatment arm and day. As this is an exploratory endpoint, these models will be explored using several methods to address missing data and model fit.

Each healthcare utilization metric within 30 days of URS will be summarized separately as a count with the associated proportion by treatment arm and tested with a chi-square test (or Fisher's exact test if event counts are 5 or less.)

In an exploratory analysis to create a composite endpoint to be used in future trials we will assess the plausibility of 2 composite measurement plans and analyses of these.

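### The primary ANCOVAs leave out the randomisation stratum (stone location), and Holm in place of the fixed 2.5% split would establish both pain endpoints more often at the same 5% error

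*Combined protocol and SAP*

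**What the plan says.** Section 7 (Subject Screening and Registration Procedures) specifies blocked, "stratified randomization based upon surgeon classified stone location (renal only versus ureteral", and Section 11.1 repeats it: "Patients will be stratified by stone location (kidney only / ureteral) and randomized".

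Section 11.4 (Analysis of the Primary Efficacy Endpoints) fits a separate ANCOVA to 7-day PROMIS pain intensity and to 7-day pain interference. In each, "treatment arm and pre-treatment (baseline) PROMIS t-score will be independent variables". Stone location is not a term. It comes up in two other places: as an example in a secondary step, where "a multivariable model will be considered to account for other patient or surgical variables that may be unbalanced", and under Sub-Group Analyses, where "A sub-group analysis by stone location is planned". The secondary analyses take over the same form: "PROMIS® Pain scores at 4 weeks will be analyzed with similar models described for the primary endpoint".

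On multiplicity, each model tests the arm effect "adjusting for baseline with a type I error of 2.5% for an overall study type I error of 5" percent, and the adjusted mean "will be reported by arm with the 97.5% confidence interval". No step-down procedure is given. Section 11.2 sizes the trial to match: 101 evaluable patients per arm for 90% power at two-sided 0.025, with a 5-point difference and SD 10. It puts a clinically meaningful change at 4 to 6 points.

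**The concern.** **Stratum.** Stratified blocking balances stone location between the arms, so the treatment estimate no longer varies because of chance imbalance in location. A model without the stratum still counts the between-location variance as residual error. If location predicts day-7 pain, the standard error is too large and the test runs below its nominal level. The optional multivariable model does not repair this. It is only to be considered, it is not the primary test, and its trigger is imbalance, which the blocking is there to prevent. It also lists timing of stent removal, which is determined after randomisation, so it is a poor vehicle for a design variable. The subgroup analysis reports results by location but leaves the overall test unchanged.

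**Multiplicity.** A fixed 2.5% per endpoint is valid and fits a rule under which either endpoint suffices. Within that rule it is not the most efficient choice. Once one endpoint is significant at 2.5%, Holm tests the other at 5%, and the family-wise error stays within 5%.

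The success rule itself is not stated. Section 5.4 words the claim as improvement in intensity and interference, and Section 11.1 joins the two hypotheses with a capitalised AND, while the split in Section 11.4 implies that either will do. If both were required, no split would be needed.

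**Working it through.** **Inputs from the plan (Sections 11.2 and 11.4):** difference 5 points, with 4 and 6 as the ends of the meaningful range; SD 10; 101 evaluable per arm; alpha 0.025 per endpoint; baseline correlation 0. **Assumptions (not in the documents):** the renal/ureteral difference d, the stratum proportions p, and the correlation between the two endpoints.

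**Step 1: the plan's own figure.** SE of the difference = 10 × √(2/101) = 1.407. Noncentrality = 5/1.407 = 3.553. The two-sided 0.025 critical value of t on 200 df is 2.258. Noncentral t power is 90.1%, so the stated 90% per endpoint is correct. For accrual, 101/0.9 = 112.2, against 112 per arm planned.

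**Step 2: stratum left out.** Between-stratum variance = p(1 − p)d², and within-stratum SD = √(100 − p(1 − p)d²). With arms balanced within strata, the true SE uses the within-stratum SD but the model without the stratum uses 10. The effective critical value is therefore 2.258 × 10/(within-stratum SD).

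Worked case, d = 5 and p = 0.5:
- Variance 0.25 × 25 = 6.25; within-stratum SD √93.75 = 9.682.
- Effective critical value 2.258 × 10/9.682 = 2.332, so true alpha is 0.021.
- Noncentrality 5/(9.682 × √(2/101)) = 3.670. Power is 90.8% without the stratum and 92.0% with it.

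| d (points), p = 0.5 | True alpha without stratum | Power without | Power with | Gain (points) |
|---|---|---|---|---|
| 0 | 0.025 | 90.1% | 90.1% | 0 |
| 2 | 0.024 | 90.2% | 90.4% | 0.2 |
| 4 | 0.022 | 90.6% | 91.3% | 0.8 |
| 5 | 0.021 | 90.8% | 92.0% | 1.2 |
| 8 (upper bound) | 0.015 | 92.0% | 94.6% | 2.6 |

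Gains are taken before rounding. With a 30:70 split they are 0.2, 0.6, 1.0 and 2.3 points for d = 2, 4, 5 and 8. A patient-level simulation (20,000 trials of 202 patients, arms balanced within strata) agrees. Null rejection without/with the stratum was 0.021/0.026 at d = 5 and 0.015/0.024 at d = 8. Power was 91.3/92.0% and 92.5/94.4%. At d = 0 to 2 there was no visible difference.

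**Step 3: fixed split against Holm.** Pairs of correlated t statistics were simulated (2,000,000 draws, noncentrality 3.553 each at 5 points). The fixed split tests each endpoint at 0.025. Holm tests the smaller p against 0.025 and then, if that is met, the other against 0.05.

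| Endpoint correlation, 5-point effect | Both, fixed split | Both, Holm | At least one (either method) |
|---|---|---|---|
| 0 | 81.2% | 88.7% | 99.0% |
| 0.5 | 83.5% | 89.6% | 96.8% |
| 0.8 | 85.8% | 90.7% | 94.5% |
| 0.9 | 87.0% | 91.2% | 93.2% |
| 0.95 | 87.9% | 91.4% | 92.3% |
| 1 | 90.1% | 90.1% | 90.1% |

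Over endpoint correlations 0 to 0.9, the chance of establishing both (fixed against Holm) is:
- 4-point effect: 51.8-65.9% against 64.5-73.7%.
- 6-point effect: 95.4-96.8% against 97.7-98.1%.
- 5-point effect, baseline correlation 0.3: 86.1-90.4% against 92.0-93.7%.
- 5-point effect, baseline correlation 0.5: 93.5-95.4% against 96.6-97.2%.

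**Step 4: error rates.** With both nulls true, the chance of any rejection is the same under the two methods: 0.0496, 0.0465, 0.0402 and 0.0361 at endpoint correlations 0, 0.5, 0.8 and 0.9. With a 5-point effect on one endpoint only, Holm wrongly rejects the other in 0.0474, 0.0451, 0.0411 and 0.0389 of trials, against 0.025 with the fixed split. All are within 5%.

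**Step 5: if both endpoints are required.** Testing each at 5% gives 88.8-94.2% power over endpoint correlations 0 to 1, against 81.2-90.1% if the split is kept.

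**The case against.** The strongest reply is that nothing in the plan is invalid. The stated power is right, the split controls the error and agrees with the sample size and the 97.5% intervals, and leaving out the stratum errs on the safe side. That is correct; both points concern efficiency and clarity.

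The stratum gain is also small and rests on assumed differences. At 2 to 5 points it is worth 0.2 to 1.2 points of power, 8 points lies beyond the plan's whole meaningful range, and the baseline score may already absorb part of any location effect. This stands as a limit on size. It is not a reason to leave out a variable that was chosen as the stratification factor and costs one degree of freedom.

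On Holm, the gain is only in establishing the second endpoint, because the chance of at least one success is unchanged. The two scores come from one questionnaire at one time point, so zero correlation is unlikely. At endpoint correlations 0.8 to 0.9 the gain at 5 points is 4.9 to 4.2 points (90.7 − 85.8 and 91.2 − 87.0), and it shrinks as baseline correlation rises. The price is a higher chance of wrongly declaring the second endpoint when only the first has an effect. All of this is true. The second endpoint still matters here, because Section 5.4 words the claim as improvement in both, and the error stays within the 5% the plan has already accepted.

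**Conclusion.** Both parts hold. The primary models leave out the randomisation stratum. The cost is a slightly conservative test and at most a few points of power: 0.2 to 2.6 for assumed location differences of 2 to 8 points with equal strata, and nothing if location is not prognostic. Type I error is not inflated, and the sample size need not change.

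The fixed split is valid but gives up power to establish both endpoints. At the design effect with baseline correlation 0, the loss against Holm is 7.5 points at endpoint correlation 0 (88.7 − 81.2), 4.2 points at 0.9, and none at 1. It is largest at the low end of the plan's meaningful range: at 4 points it is 12.7 points at correlation 0 (64.5 − 51.8) and 7.8 at 0.9 (73.7 − 65.9). That Holm rejects everything the fixed split rejects, within the same 5%, depends on none of these assumptions; only the sizes do. The plan also needs to say whether one endpoint suffices or both are required.

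**What to change.** 1. Add stone location, as recorded at randomisation, as a fixed effect in both primary ANCOVAs and in the analogous secondary models (4-week PROMIS pain and LURN SI-10).
2. State in one sentence that either primary endpoint suffices, and use Holm: the smaller p-value against 0.025, then the other against 0.05. If the sponsor instead requires both, test each at 5% with no split. Bring Sections 5.4, 11.1 and 11.4 into line with the rule chosen.
3. Say which intervals accompany the tests. The planned 97.5% intervals are given by arm and do not correspond exactly to Holm's second step; a 97.5% interval for the difference could include zero for an endpoint declared there.

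The cost is wording and one degree of freedom per model. The stratum is already collected, and no patients or visits are added. Under Holm the sponsor accepts a 3.9-4.7% chance, instead of 2.5%, of wrongly declaring the second endpoint when only the first has an effect. Because the analysis plan is part of the protocol, Section 3 requires IRB approval of the change. It should be in place before the interim comparison by arm at 112 patients.

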Immediate. Based upon prior RCT outside of the United States, the use of silicone ureteral stents has the potential to decrease pain and LUTS after URS.(12) Decreased pain and LUTS after URS secondarily could decrease the rate of ambulatory healthcare utilization, opioid prescriptions, postoperative ED visits, and unplanned hospitalizations. It could also decrease the number of days required to miss work due to recovery.

Long-range. Decreased pain and LUTS after URS secondarily could decrease a patient's exposure to opioid analgesia postoperatively. Less patient requirements for opioid analgesia could decrease the incidence of new persistent long-term use of opiates in these patients.

Section 5: STUDY OBJECTIVES**Section 5.1: Primary Objectives**

1. To determine the health-related quality of life and symptoms in patients with urinary stone disease stented with silicone or polyurethane stents at ureteroscopy.

Section 5.2: Secondary Objectives

1. To compare 30-day emergency department visits and hospitalization rates between study arms
2. To compare rates and intensity of ambulatory healthcare encounters after ureteroscopy and stenting between study arms
3. To compare stone-free rates between study arms
4. To compare abnormal imaging findings after ureteroscopy and stenting between study arms

Section 5.3: Exploratory Objectives

1. To compare days taken off work by patient between study arms
2. To compare days taken off work by caregiver between study arms
3. To compare Ecological Momentary Assessments (EMA) measured via daily text message for 10 days between study arms
4. To compare Composite score difference between Winratio and Desirability Of Outcome Ranking (DOOR) between study arms
5. To compare number of patients receiving opioid prescriptions between study arms
6. To compare ICIQ-s score at 7 days between study arms
7. To compare ICIQ-s score at 4 weeks between study arms

Section 5.4: Endpoints

- Primary Efficacy Endpoint(s):
 - Silicone stent placement will be associated with significantly improved PROMIS® scores of pain intensity and interference at 7 days compared to non-silicone stent placement.
- Secondary Efficacy Endpoint(s):
 - Silicone stent placement will be associated with equivalent PROMIS® scores of pain intensity and interference at 4 weeks compared to non-silicone stent placement.

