A clinically meaningful change in pain PROMIS® score is between 4 and 6 and the standard deviation of the score is 10(16-18). Assuming a 5 t-score PROMIS® pain point difference between 2 arms and a standard deviation of 10, a t-test including 101 patients per arm has 90% power with a 2-sided alpha = 0.025. Assuming a 10% loss-to-follow-up, accrual of 224 study treated patients (112 patients per arm) is planned. Our planned analysis does not match this calculation because we will adjust for the baseline pain to ensure any imbalance prior to surgery is accounted for. However, this power calculation, by ignoring the adjustment of baseline pain, is accurate if the correlation of baseline pain with our outcome is 0. If the correlation is greater than 0, then we will have more power than described.(19)

Section 11.3: Populations for Analyses

Modified Intent-to-Treat (m-ITT) Population: All participants eligible and randomized who complete the pain intensity and pain interference questionnaire between 7-10 days post-URS will be included.

Subjects will be analyzed by assigned treatment at randomization. This is the main population for efficacy analyses.

Per-Protocol Population: All Patients eligible and randomized patients who complete the pain intensity and pain interference questionnaire between at 7 days post-URS will be included per treatment arm received. This second population will be used to assess the robustness of the primary and secondary efficacy outcomes.

Safety Population: All patients who are randomized and receive a stent will be define the safety population and used for all safety analyses. Subjects will be analyzed by assigned treatment arm.

Section 11.4: Statistical Analyses

General Approach

Descriptive statistics for the study population will be reported using frequentist statistics. In general, continuous measures will be reported using means and standard deviations or medians and the interquartile range as the distribution warrants. Categorical variables will be reported as counts and proportions.

Analysis of the Primary Efficacy Endpoints

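### The fixed 2.5%/2.5% split for the two primary pain endpoints is valid, but Holm's procedure would give more power for each endpoint and for both at the same 5% overall error

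*Combined protocol and SAP*

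**What the plan says.** Section 11.4 (Analysis of the Primary Efficacy Endpoints) sets out two primary outcomes: "The primary endpoints of the study are PROMIS® pain intensity and PROMIS® pain interference t-scores. Each endpoint will be analyzed separately using an ANCOVA model". Each model tests treatment arm adjusted for baseline, "with a type I error of 2.5% for an overall study type I error of 5" percent, and adjusted arm means are reported with 97.5% confidence intervals. No section provides a step-down, alpha-recycling or hierarchical rule.

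Section 11.2 sizes the trial at the same level, for a difference of 5 points and an SD of 10: "a t-test including 101 patients per arm has 90% power with a 2-sided alpha = 0.025". To allow for dropout, the section then adds: "Assuming a 10% loss-to-follow-up, accrual of 224 study treated patients (112 patients per arm) is planned". The calculation leaves out the baseline adjustment: "Assume that the correlation of baseline is 0 for purposes of the sample size calculation".

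Section 5.4 states the primary claim over both scores: "Silicone stent placement will be associated with significantly improved PROMIS® scores of pain intensity and interference at 7 days". Section 11.1 joins the two hypothesis pairs with AND. No section says whether the trial succeeds on one endpoint or needs both.

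The only interim look (Sections 10.5 and 11.4, after 112 patients) is for futility, so it spends no efficacy alpha.

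**The concern.** Under a fixed split, the 2.5% assigned to one endpoint is lost to the other even after the first has been rejected. Holm's procedure passes it on: once the smaller p-value is below 2.5%, the other endpoint may be tested at 5%, and the family-wise error stays at or below 5% whatever the correlation.

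For example, take p = 0.001 for intensity and p = 0.03 for interference. The plan must call interference non-significant. Holm would declare it, with the same overall error guarantee. What is at stake is the chance of supporting the second of two primary claims in a trial whose stated claim names both.

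**Working it through.** **Inputs.** Difference 5, SD 10, 101 evaluable per arm, two-sided alpha 0.025 per endpoint, baseline correlation 0 (Section 11.2); overall alpha 0.05 (Section 11.4); 1:1 allocation (Section 7). The correlation between the two endpoints is not in the documents, so it is an assumption, varied from 0 to 0.9. The same 5-point effect is assumed on both endpoints.

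**Step 1: reproduce the plan.** Non-centrality = (5/10) × √(101/2) = 3.553, with 200 degrees of freedom. Exact t-test power at two-sided 0.025 is 90.1% with 101 per arm and 89.8% with 100, so 101 is right. Dropout: 101/0.9 = 112.2, in line with the stated 112. Alpha: 2 × 0.025 = 0.05. The stated figures hold.

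**Step 2: compare the rules.** Correlated normal test statistics with mean 3.553 were simulated, 2 million draws per setting, against t critical values 2.258 (2.5%) and 1.972 (5%). This approximation gives 90.2-90.3% per endpoint, against the exact 90.1%.

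| Endpoint correlation | Each: split | Each: Holm | Both: split | Both: Holm | At least one: either rule |
|---|---|---|---|---|---|
| 0 | 90.3% | 93.9% | 81.5% | 88.8% | 99.1% |
| 0.5 | 90.3% | 93.3% | 83.6% | 89.7% | 96.9% |
| 0.7 | 90.3% | 93.0% | 85.0% | 90.4% | 95.5% |
| 0.8 | 90.2% | 92.7% | 85.9% | 90.8% | 94.5% |
| 0.9 | 90.2% | 92.3% | 87.2% | 91.3% | 93.3% |

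Hand check at correlation 0, where power for one endpoint is 0.9026 at 2.5% and √0.8897 = 0.9432 at 5%:

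- Split, both: 0.9026² = 0.815.
- Holm, both: both significant at 5%, less the case where both p-values lie between 2.5% and 5%. This is 0.8897 − (0.9432 − 0.9026)² = 0.8897 − 0.0016 = 0.888.
- Holm, each: 0.9026 + 0.9026 × 0.0406 = 0.939.

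**Step 3: error rate.** With no effect on either endpoint, the chance of any false rejection is the same under both rules: 4.7% at correlation 0, 3.5% at 0.9. With a 5-point effect on one endpoint only, the false rejection rate for the other is about 2.4% under the split and 3.8-4.6% under Holm. All are within 5%.

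**Step 4: sensitivity.**

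- Difference of 4 (low end of the 4 to 6 range in Section 11.2): each endpoint goes from 72% to 76-78%, both from 52-66% to 65-74%.
- Baseline correlation above 0 (assumed; SD becomes 10 × √(1 − r²)). At r = 0.3, both goes from 86-90% to 92-94%, a gain of about 3-6 points. At r = 0.5, both goes from 94-95% to 97%, a gain of about 2-3 points.
- If success requires both endpoints, no split is needed. Testing each at 5% gives joint power of 89.0% (correlation 0) to 92.3% (0.9), slightly above Holm.

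**The case against.** The strongest reply is that nothing here is wrong. The split is pre-specified, controls the family-wise error and matches the sample size. That stands, and this point should not be read as a validity defect.

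A reader might go further and infer that the 90% is overstated because the joint power is lower. The documents do not support that: Section 11.2 speaks of power for each hypothesis and never claims 90% for both. Nor would it be fair to quote a seven-point gain as the expected benefit. That figure needs uncorrelated endpoints and a baseline that predicts nothing. Both scores come from one pain questionnaire (Figure 1), so substantial correlation is likely, and Section 11.2 itself says that any baseline correlation adds power.

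The undefined success rule also matters. If either endpoint suffices, Holm leaves the chance of trial success unchanged. If both are required, testing each at 5% is slightly better than Holm. Holm is the natural rule when the two claims are made separately, which is how Section 11.4 treats them. Under neither of the last two readings is the fixed split the most efficient valid rule.

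Finally, a fixed split pairs naturally with 97.5% intervals, and preferring that agreement is legitimate. Its weight is limited here because Section 11.4 attaches the 97.5% intervals to the arm means, not to the treatment difference that is tested.

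**Conclusion.** The point holds as an available efficiency gain. At the plan's own inputs, Holm adds about 2-4 points of power per endpoint and about 4-7 points for declaring both, with the family-wise error still at most 5%. At endpoint correlations of 0.7-0.9 the gain for both is about 4-5 points. It shrinks further as baseline pain becomes more predictive and is larger if the true difference is 4. The chance of winning at least one endpoint is unchanged.

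These sizes rest on an equal effect on both endpoints, a common SD of 10, 101 evaluable patients per arm and an assumed endpoint correlation. That Holm never rejects less than the split rests on none of these.

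**What to change.** In Section 11.4, replace the fixed split with Holm: test the smaller of the two p-values at 2.5% and, if it is rejected, test the other at 5%. In Section 11.2, give the joint power beside the per-endpoint 90%, with the endpoint correlation assumed. State whether success needs one endpoint or both; if both, test each at 5% instead (joint power 89-92%).

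Make the change before any unblinded comparison of the arms, including the interim after 112 patients, which compares pain between arms.

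The cost is a few sentences, with no extra patients or data. The one small downside is that a 97.5% interval for the second endpoint's treatment difference may include zero although Holm declares that endpoint. The SAP should say that the test decision, not the interval, governs.
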